[name]
[name]
Phone: [name]
[contact]
www.ProstateLaserCenter.com

MRI Guided Transrectal Prostate Laser Ablation for Benign Prostatic Hypertrophy (BPH)

NCT03131544

04/07/2017

[name]
[name]
Phone: [name]
[contact]
www.ProstateLaserCenter.com

Protocol Number: Prostate Laser Center BPH 01
Principal Investigator: **[name]**
MRI Guided Transrectal Prostate Laser Ablation for BPH

Over 100,000 BPH procedures are performed annually in the US. The purpose of this study is to evaluate the effectiveness of performing MRI guided transrectal laser ablation using a 980 nm laser (Visualase™ by Medtronic, Inc., a Minnesota, U.S.A. company) to treat benign prostatic hypertrophy (BPH). The laser system will be used to necrotize urological soft tissue within the prostate under MRI guidance. This will be a single center, single arm prospective trial with an anticipated enrollment of 10 men. Patients who elect this treatment option and choose to be part of the study will be enrolled consecutively.

https://www.accessdata.fda.gov/cdrh_docs/pdf7/K071328.pdf

“The Visualase Thermal Therapy System is indicated for use to necrotize or coagulate soft tissue through interstitial irradiation or thermal therapy under magnetic resonance imaging (MRI) guidance in medicine and surgery in cardiovascular thoracic surgery (excluding the heart and the vessels in the pericardial sac), dermatology, ear-nose-throat surgery, gastroenterology, general surgery, gynecology, head and neck surgery, neurosurgery, plastic surgery, orthopedics, pulmonology, radiology, and urology, for wavelengths 800nm through 1064 nm.”

Primary outcome measures at baseline, 2 months, 4 months, 6 months and 24 months:

- 1) Change in International Prostate Symptom Score
- 2) Change in International Prostate Symptom Score Quality of Life Question
- 3) Change in BPH Impact Index
- 4) Change (or lack thereof) in Sexual Health Inventory of Men (SHIM) score
- 5) Number and severity of adverse events

Inclusion Criteria:

- 1) Diagnosis of lower urinary track symptoms (LUTS).
- 2) Prostate volume of 40 – 200 cc.
- 3) Men \geq 45 years old.
- 4) IPSS \geq 15
- 5) BPH Impact Index \geq 5.

Exclusion Criteria:

- 1) History of prostate or bladder cancer, pelvic radiation, untreated bladder stones, or findings suggestive of likely underlying prostate cancer.
- 2) Need to catheterize to relieve obstruction.

[name]
[name]
Phone: [name]
[contact]
www.ProstateLaserCenter.com

- 3) Daily use of incontinence materials/padding.
- 4) Neurogenic or hypotonic bladder, Parkinson's Disease, or a history of uncontrolled diabetes.
- 5) Prior interventional or surgical treatment of BPH.
- 6) Penile prosthesis.
- 7) Artificial urinary sphincter or collagen bladder injection.
- 8) Urethral stricture.
- 9) Bleeding disorder/coagulopathy.
- 10) Inability to refrain from blood thinners in the peri-procedural period.
- 11) Inability or chooses not to provide informed consent.
- 12) Any serious medical condition which would make proceeding to treatment unsafe.
- 13) Significant contraindication to MRI or gadolinium contrast.
- 14) Hip replacement.
- 15) Lack of a rectum.
- 16) Life expectancy of less than two years.
- 17) Unable or unwilling to complete all required questionnaires and follow-up assessments.

Data Collection:

Patients will complete the follow-up surveys at home and mail, fax, or scan and e-mail them in. They will fill up survey forms related to their SHIM, IPSS with QOL, and BPH Impact Index (as described in the outcome measures).

Statistical Analysis:

We will perform a repeat analysis of variance (rANOVA) on each patient's survey results for all timepoints. Pairwise p-values between pre-ablation and subsequent timepoints will be calculated.

Risk / Safety Information:

Patients will also be consented with the general treatment, specific procedure and sedation consent forms, included. Risks are described in those documents.

Unanticipated problems will be reported to the IRB office.

I am establishing a physician-patient relationship with those participating in the study. I will manage medical complications should they arise and involve physicians of other specialties as needed.

Monitoring and reporting of Adverse Events:

[name]
[name]
Phone: [name]
[contact]
www.ProstateLaserCenter.com

The Investigator will be responsible for overseeing the project and will monitor all adverse events. Any event deemed to be an “unanticipated problem” as defined by the IRB will be reported to the IRB as required. The principal investigator and his staff will be in regular communication with patients and patients will be instructed to self report adverse events.

Informed consent:

Each participant will have ample time to review the informed consent and ask questions prior to signing the document. Each participant will receive a copy of the signed informed consent.

Confidentiality:

The data will be compiled into an encrypted excel spreadsheet that is only accessible on encrypted computers requiring secure log-in and via online access (Office 365) requiring secure log-in. Only the principle investigator and staff that has been HIPAA trained and signed the study confidentiality form will have access to the data.

Intended Use of Data:

The intention is to publish the data in a peer reviewed journal and on ClinicalTrials.gov. The data will be de-identified and compiled prior to publication. MRI images without any identifiers will also be published.

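### With no survey between 6 and 24 months and no missing-data rule, the 24-month change may be overstated if men who worsen return fewer forms; a supportive 12-month form with an all-available-data model would help modestly

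*Combined protocol and SAP*

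**What the plan says.** The outcome list in the combined protocol and SAP is headed "Primary outcome measures at baseline, 2 months, 4 months, 6 months and 24 months". It covers IPSS, the IPSS quality-of-life question, the BPH Impact Index, SHIM and adverse events. Three of the four follow-up times fall in the first 6 months, and the next comes 24 − 6 = 18 months later.

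Under Data Collection, "Patients will complete the follow-up surveys at home and mail, fax, or scan and e-mail them in". No reminder or retrieval step is described.

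Under Statistical Analysis, "We will perform a repeat analysis of variance (rANOVA) on each patient's survey results for all timepoints", and "Pairwise p-values between pre-ablation and subsequent timepoints will be calculated". Nothing is said about a form that does not come back: no carrying forward, no imputation and no expected rate of loss. No responder or relapse is defined; the symptom outcomes are change scores.

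The opening section states: "This will be a single center, single arm prospective trial with an anticipated enrollment of 10 men".

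Two provisions bear on the gap. Exclusion criterion 17 removes men "Unable or unwilling to complete all required questionnaires and follow-up assessments". The adverse-event section commits the investigator and staff to regular contact with patients and adds that "patients will be instructed to self report adverse events".

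**The concern.** Month 24 is the only evidence on whether the effect lasts. A man who worsens at, say, 12 months and does not send in the last form leaves no survey score that records the worsening. A classical repeated-measures ANOVA drops him altogether, so the men analysed are a selected group at the earlier timepoints as well. A mixed model keeps him but predicts his month 24 largely from his early, good scores. Neither approach can separate him from a man whose improvement held.

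With 10 men and no control arm, one or two such losses are enough to move the mean, and nothing else in the design would show that it had happened. Because surveys are already completed at home, a mid-course form would need no visit or procedure.

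**Working it through.** **Inputs from the documents.** Surveys at 0, 2, 4, 6 and 24 months; 10 men, single arm; repeated-measures ANOVA with comparisons against baseline; no missing-data rule. The documents give no effect size, SD, relapse rate or non-return rate, so there is no planned figure to reproduce.

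**Assumptions (not in the documents).** Mean IPSS change at 6 months is −12. A share *p* of men later lose *R* points. The 24-month form is missing in a share *m_r* of relapsers and *m_n* of the others.

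**Step 1: expected bias with data to 6 months only.** The share of relapsers among returned 24-month forms is

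p_obs = p(1 − m_r) / [p(1 − m_r) + (1 − p)(1 − m_n)].

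The true mean change is −12 + R·p and the observed mean is −12 + R·p_obs, so the bias is −R(p − p_obs). A negative value overstates the improvement. If relapse is unrelated to the 6-month score, as assumed here, a model adjusting for that score has the same bias.

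Central case, p = 0.30, R = 8, m_r = 0.70, m_n = 0.10: p_obs = 0.09 / (0.09 + 0.63) = 0.125, and the bias is −8 × (0.30 − 0.125) = **−1.40**. Overall, 28% of forms are missing.

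| p | R | m_r | m_n | p_obs | Bias (IPSS points) |
|---|---|---|---|---|---|
| 0.20 | 8 | 0.50 | 0.10 | 0.10/0.82 = 0.122 | −0.62 |
| 0.30 | 8 | 0.70 | 0.10 | 0.09/0.72 = 0.125 | −1.40 |
| 0.40 | 8 | 0.70 | 0.10 | 0.12/0.66 = 0.182 | −1.75 |
| 0.30 | 10 | 0.50 | 0.10 | 0.15/0.78 = 0.192 | −1.08 |
| 0.30 | 10 | 0.20 | 0.20 | 0.24/0.80 = 0.300 | 0 |
| 0.30 | 10 | 0.10 | 0.30 | 0.27/0.76 = 0.355 | +0.55 |

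The last two rows show that the direction depends on who fails to reply.

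**Step 2: the same in whole men.** Take 10 men, of whom 3 relapse by 10 points. The true change is (7 × −12 + 3 × −2)/10 = −9.0. If one relapser is missing, the complete-case mean is (−84 − 4)/9 = −9.78, an overstatement of 0.78. If two are missing it is (−84 − 2)/8 = −10.75, an overstatement of 1.75.

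**Step 3: what a 12-month form changes.** These results are simulated.

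- *Complete-case ANOVA:* nothing. With p = 0.30, R = 10, m_r = 0.50 and m_n = 0.10, the bias is −1.08 with or without the form.
- *Regression on observed scores, large sample, central case:* with 70% of relapses visible by month 12 and every man returning the 12-month form, the bias falls from about 1.4 to 0.9 points.
- *Likelihood model with compound symmetry, 10 men, same case:* the bias falls from about 1.38 to 1.19, and root-mean-square error from 2.41 to 2.30.
- *Dependence on who returns the 12-month form* (R = 10 scenario, half of relapses visible by month 12, model assuming data missing at random): 1.08 falls to 0.82 if all the men later lost return it and to 0.93 if half do. There is no gain if none do.

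**Step 4: the baseline-score sensitivity analysis.** In Step 2 with two men missing, setting both to a change of 0 gives −86/10 = −8.6. Together with the complete-case −10.75 this brackets the true −9.0. The bracket holds here because no missing man is worse than at baseline.

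**The case against.** The strongest case against is that the bias is conditional and the remedy weak. The bias exists only if relapsers reply less often, and the documents give no figure for this. An extra form achieves nothing under the planned ANOVA on complete cases, where another timepoint is another chance to lose a man. At this sample size an over-flexible model can do harm: regression on the individual scores with 10 men raised root-mean-square error from about 2.6 to 3.6 when the 12-month score was added, and was closer to the truth in only 53% of simulated trials. All of this stands. It is why the claim is worded as a possibility and why the form is worth adding only together with a model of simple covariance structure.

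It can also be said that exclusion criterion 17 and the promised regular contact already cover the gap. They help, but only in part. The criterion screens willingness at entry and does not retrieve a form two years later. The contact is described under adverse-event monitoring and collects no symptom score.

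That same clause does limit the safety side. A reader might infer that adverse events go unmonitored for 18 months. The documents do not support this: contact and self-report are ongoing and not tied to survey dates. A 12-month form would add only a structured prompt.

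**Conclusion.** The point holds as a modest, low-cost improvement. The survey gap, the self-returned forms and the missing rule for non-return are all in the text, and with 10 men they leave the 24-month change open to informative non-return. In the assumed scenarios where relapsers reply less often, the overstatement is roughly 0.6 to 1.75 IPSS points. It is zero under equal non-return, and the benefit is understated if satisfied men stop replying.

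Three stronger readings are not supported. The 24-month result cannot be said to *be* overstated, since no relapse or return rates are given. Lost men would not be counted as 6-month responders, since the plan neither carries scores forward nor defines a responder. A 12-month form would not by itself correct the problem: with the mixed model the expected reduction for 10 men is about 0.2 points (1.4 to 1.2), and only if the men later lost return that form.

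**What to change.** - Add a 12-month survey (IPSS, quality-of-life question, BPH Impact Index, SHIM and structured adverse-event questions) by the existing at-home route. Label it supportive, with no additional primary p-value.
- Replace complete-case repeated-measures ANOVA with a likelihood-based mixed model that has a simple covariance structure, such as compound symmetry, and uses every returned form. Adopt this and the 12-month survey together.
- Report the number of forms returned at each timepoint, and show individual trajectories.
- Add a sensitivity analysis in which men without a 24-month form are given their baseline score.

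The cost is one more form per man (10 in all), slightly more patient burden, and a short protocol and IRB amendment. The return counts, trajectories and sensitivity analysis need no new data, and are worth having even if the 12-month survey is not adopted.

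### SHIM is a primary outcome that names lack of change as a possible result, but the planned tests can only detect a change

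*Combined protocol and SAP*

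**What the plan says.** The introductory paragraph describes a "single center, single arm prospective trial with an anticipated enrollment of 10 men". The outcome list is headed "Primary outcome measures at baseline, 2 months, 4 months, 6 months and 24 months", which gives four comparisons with baseline for each scale. Item 4 is "Change (or lack thereof) in Sexual Health Inventory of Men (SHIM) score". The other three questionnaire outcomes (IPSS, its quality-of-life question and the BPH Impact Index) are listed simply as changes, so SHIM is the only scale for which absence of change is named.

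The Statistical Analysis section has two sentences. The first plans a repeated-measures ANOVA on the survey results over all timepoints. The second reads: "Pairwise p-values between pre-ablation and subsequent timepoints will be calculated". Neither that section nor any other states a confidence interval, margin, significance level or rule for reading a non-significant result.

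**The concern.** The ANOVA tests equality of means over time, and each pairwise p-value tests a zero difference from baseline. Rejection supports a change. Non-rejection can mean that nothing changed or that the data were too few to tell, and a p-value alone does not separate the two. One of the two results named in the SHIM outcome therefore has no planned analysis that can support it.

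The stake is how the result will be read. Under Intended Use of Data the plan says: "The intention is to publish the data in a peer reviewed journal and on ClinicalTrials.gov". A report that SHIM did not change significantly could be taken to mean that the procedure spares sexual function. As written, the reading of a non-significant SHIM result is left open until the data are known.

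**Working it through.** **Nothing to reproduce.** Enrolment of 10 is given without a power calculation, effect size or SD. The logical point needs no arithmetic; the figures below show how much it could matter.

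**From the documents:** n = 10; single arm; SHIM at baseline and at 2, 4, 6 and 24 months.

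**Assumed, not in the documents:** two-sided alpha 0.05; all 10 men assessed; each visit compared with baseline by a paired t-test; SD of SHIM change between 2 and 7 points; a 3-point fall as an illustration only, not as a threshold for clinical importance.

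**Step 1, precision.** Half-width of the 95% CI = t(0.975, 9 df) × SD / √10 = 2.262 / 3.162 × SD = 0.7154 × SD.

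**Step 2, an observed fall with p just above 0.05.** The mean fall is then about one half-width, so the interval runs from about zero to a fall of 2 × half-width.

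**Step 3, chance of missing a true 3-point fall.** This is the probability of p > 0.05 in one pairwise test, from the non-central t distribution with 9 df and non-centrality 3 × √10 / SD = 9.487 / SD.

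| SD of change | Half-width | Far CI limit when p ≈ 0.05 | Non-centrality | Misses a 3-point fall |
|---|---|---|---|---|
| 2 | 1.43 | 2.86 | 4.74 | 1.3% |
| 3 | 2.15 | 4.29 | 3.16 | 19.7% |
| 4 | 2.86 | 5.72 | 2.37 | 43.8% |
| 5 | 3.58 | 7.15 | 1.90 | 60.4% |
| 6 | 4.29 | 8.58 | 1.58 | 70.7% |
| 7 | 5.01 | 10.01 | 1.36 | 77.2% |

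**Step 4, what p > 0.05 conveys.** With no true change, p > 0.05 occurs 95% of the time at every SD. At SD 2 the contrast with a true 3-point fall is 95% against 1%; at SD 7 it is 95% against 77%. The same non-significant p-value is informative about a 3-point fall in the first case and nearly uninformative in the second. The width of the interval shows which case applies.

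**Step 5, what a preservation claim would require.** Suppose the claim is made only when the lower limit of the 95% CI for mean change lies above minus a pre-set margin. If the true change is zero, the rule succeeds with probability P(T > 2.262), where T is non-central t with 9 df and non-centrality (margin / SD) × √10. The result is 29% for a margin of 0.5 SD, 56% for 0.75 SD, 80% for 1.0 SD and 99% for 1.5 SD. About 80% success needs a margin of roughly one SD, which is 2 to 7 points over the assumed range.

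**Sensitivity.** With 8 men assessed, the half-width is 0.836 × SD, or 1.7 to 5.9 points.

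**The case against.** The strongest reply is that the list gives outcome measures, not hypotheses. The parenthesis in item 4 may be only a neutral remark that SHIM, unlike the symptom scales, is not expected to improve. The stated aim supports this: "The purpose of this study is to evaluate the effectiveness of performing MRI guided transrectal laser ablation". A reader might infer that the trial sets out to prove preserved sexual function and fails. The documents do not support that, because they contain no such hypothesis and no margin. This part of the objection stands and limits the point to a mismatch.

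A reader might also infer that only p-values will be published. The plan does not say so. Mean changes may well be reported, and from a mean change, n and an exact paired p-value a reader could recover the interval. That would fail if p were given only as non-significant, and would need adapting if the comparisons used a pooled ANOVA error. The plan commits to neither an estimate nor an interval.

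Nor do the documents support saying that the trial is underpowered for SHIM. The miss rate runs from 1% to 77% on assumed SDs, so the size of the problem is not established.

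Two further objections are sound. The missing interval affects all four scales, so the remedy should cover all four. And an interval does not prove lack of change; it only limits how large a change remains plausible. Deleting the parenthesis would remove the mismatch in wording, but would still leave no stated reading of a non-significant SHIM result.

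**Conclusion.** The point holds in a narrow form. Outcome 4 names two possible results, and the planned tests can support only one. This follows from the null hypothesis of both tests and does not depend on the assumed figures. Non-significance alone would not establish absence of change in a larger trial either; with 10 men the interval may simply be too wide to exclude a fall that matters.

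The illustrated size (half-width 1.4 to 5.0 points; a 3-point fall missed 1% to 77% of the time) rests on the assumed SD range, alpha and complete follow-up. The gap affects how one primary outcome can be interpreted, not the validity of the trial as a whole. It is worth correcting because the correction is cheap.

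**What to change.** Add to the Statistical Analysis section, in substance:

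> For SHIM and the other three scales, mean change from baseline with a two-sided 95% confidence interval will be reported at 2, 4, 6 and 24 months, alongside the p-values. A non-significant p-value for SHIM will not be interpreted as no change. The conclusion on SHIM will be limited to the changes that the confidence interval excludes.

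A margin is needed only if the sponsor wants to claim that SHIM is preserved. In that case one margin and one timepoint should be fixed and justified before enrolment. The claim should be made only if the lower confidence limit lies above minus the margin, and the result reported as inconclusive otherwise.

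Individual SHIM scores need not be listed. In a single-centre series of 10 men that would sit uneasily with the commitment that "The data will be de-identified and compiled prior to publication".

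The cost is two or three sentences, with no extra patients, visits or data. The drawback is that SHIM may be reported as inconclusive, and with 10 men a preservation claim would be hard to reach unless the margin is about one SD of the change score or more.

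### The only stated inference is p-values against zero change, which cannot carry the effectiveness aim, and the plan lets the form that qualifies a man for entry also serve as his baseline

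*Combined protocol and SAP*

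**What the plan says.** The opening paragraph gives the aim: "The purpose of this study is to evaluate the effectiveness of performing MRI guided transrectal laser ablation". It describes a "single arm prospective trial with an anticipated enrollment of 10 men" and adds: "Patients who elect this treatment option and choose to be part of the study will be enrolled consecutively".

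The outcome list is headed "Primary outcome measures at baseline, 2 months, 4 months, 6 months and 24 months". It names change in IPSS, in the IPSS quality-of-life question, in BPH Impact Index and in SHIM, together with adverse events. Items 4 and 5 of the Inclusion Criteria require an IPSS of at least 15 and a BPH Impact Index of at least 5.

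The Statistical Analysis section is two sentences: the rANOVA over all timepoints, and "Pairwise p-values between pre-ablation and subsequent timepoints will be calculated". It gives no confidence interval, comparator, benchmark, success rule or limit on interpretation.

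The plan speaks of baseline in the outcome list and of pre-ablation in the analysis. It does not say when that form is completed or whether it is the one used for eligibility. Data Collection covers only later forms: "Patients will complete the follow-up surveys at home and mail, fax, or scan and e-mail them in".

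**The concern.** Two matters of unequal weight arise.

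First, every planned test compares the same men with themselves and takes zero change as its null. A small p-value then shows that scores moved. It does not separate the ablation from placebo response, natural fluctuation or other care. IPSS, its quality-of-life question and BPH Impact Index are self-reported by men who know they were treated, so they are the outcomes most exposed. Intended Use of Data foresees a journal article and a ClinicalTrials.gov posting. A report built only on the stated analysis could present a p-value as evidence of effectiveness.

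Second, a man who must score above a threshold to enter is more likely to be entered on a day when he scores high. If that same form is his baseline, his next score is expected to be lower even if nothing has happened to him. This applies directly to IPSS and BPH Impact Index. The quality-of-life question and SHIM have no entry cut-off, and adverse events have no planned test, so they fall outside this second matter.

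**Working it through.** **No plan figure to reproduce.** The enrolment of 10 comes without alpha, power, effect size or SD. Everything below except n = 10 and the two cut-offs is assumed. Tests are taken as paired t, two-sided 5%, counted in the direction of improvement (nominal 2.5%).

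**Step 1: what the tests address.** The rANOVA null is equal means at the five timepoints. The pairwise null is zero mean change. Neither contains a term for what would have happened without ablation, and a larger n does not add one.

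**Step 2: regression to the mean if the qualifying form is the baseline.** For an unselected population with mean μ, standard deviation SD and reliability r, and with z = (c − μ)/SD:

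expected fall = SD × (1 − r) × φ(z) / (1 − Φ(z))

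Scores are whole numbers, so a cut-off of 15 acts as c = 14.5.

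- Upper end (μ 14, SD 7, r 0.7): z = 0.5/7 = 0.071; φ/(1 − Φ) = 0.398/0.4715 = 0.844; fall = 7 × 0.3 × 0.844 = 1.77.
- Lower end (μ 24, SD 6, r 0.9): z = −9.5/6 = −1.583; φ/(1 − Φ) = 0.114/0.943 = 0.121; fall = 6 × 0.1 × 0.121 = 0.07.

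Simulation of integer scores from 0 to 35, with independent errors between forms and no treatment effect, agrees (1.78 and 0.08):

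| Unselected IPSS mean | Expected fall, points | Significant improvement, n = 10 |
|---|---|---|
| 14 | 0.5–1.8 | 8–17% |
| 17–20 | 0.2–1.2 | 4–10% |
| 22–24 | 0.1–0.6 | 3–5% |

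For BPH Impact Index (0 to 13, unselected mean 5–8, SD 2.5–3, same reliabilities) the fall is 0.04–0.64 points and the rate 3–13%. At mean 8 these are 0.04–0.21 points and 3–5%.

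The size follows the inputs. Mean 12, SD 7 and reliability 0.6, with the formula applied at c = 15, give 3.05 points.

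**Step 3: a separate baseline form.** With independent errors, the mean change returns to zero and the rate to 2.5%. If errors on the qualifying and separate forms correlate at ρ, about ρ times the bias remains. In the worst IPSS setting that is 0.3 × 1.78 = 0.53 points and 0.5 × 1.78 = 0.89 points.

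**Step 4: precision of the interval.** The half-width at n = 10 is 2.262 × SD of change/√10 = 0.715 × SD of change. For a change SD of 2.7 to 5.4 (the range found in step 3, rounded) this is ±1.9 to ±3.9 IPSS points.

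**The case against.** The single arm is declared, the outcomes are worded as change, and the analysis tests change, so test and outcome match. No passage says that a p-value will be read as proof of effectiveness, and the harm would arise only in a later report. A confidence interval is no more controlled than a p-value. All of this stands. What remains is that the aim is effectiveness and the plan neither asks for an interval nor limits the conclusion.

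Four stronger readings are tempting, and the documents support none of them.

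- *The sample of 10 causes the attribution problem.* It does not. Any single arm has it, and the small n affects only precision.
- *The error rate is grossly inflated.* Suppose a 3-point fall unrelated to ablation. The pairwise test then rejects in about 35–88% of trials (change SD 5.4 to 2.7). That is power to detect a change that was assumed, where the tested null is false. It is not a type I error rate, and the documents give no figure for such a fall.
- *The plan names no estimate.* Change in each scale is the named outcome. The gap is narrower: an interval and a sentence on interpretation.
- *The qualifying form is the baseline.* The text does not say so. It only fails to exclude it.

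On size, men who choose a procedure may well score far above the cut-off, where the bias nearly vanishes. The 1.8-point and 17% figures need an unselected mean of 14, below the cut-off. This too stands, and it keeps the second matter small.

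**Conclusion.** The point holds as a minor one, in two parts.

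The stated p-values test change over time and cannot alone answer the effectiveness question. This rests on the text and on no assumed figure. It is a limit on what may be concluded, not an error in choosing a single arm.

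The undefined baseline leaves room for an avoidable upward bias on two primary scales. It is conditional on the qualifying form being used. For IPSS it is then about 0.1 to 1.8 points, with a false-positive rate of 3–17% against 2.5%, and it is close to nominal at unselected means of 22–24. Those sizes depend on the assumed mean, SD and reliability and on independent errors at follow-up, so they illustrate the problem and do not predict its size in this trial.

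**What to change.** 1. In Statistical Analysis, add that mean change with a 95% confidence interval will be reported at each timepoint beside any p-value, and that conclusions will be stated as uncontrolled change from baseline. The interval does not supply a control. It lets readers weigh the size of the change against plausible non-specific improvement. This costs only wording.

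2. In Data Collection, define the baseline as an IPSS, quality-of-life and BPH Impact Index form completed on a separate day after eligibility is confirmed and before ablation, without applying the cut-offs again. If such a form is already taken, one sentence is enough. Otherwise it costs one extra questionnaire per man (10 in all), a small scheduling constraint, a slightly larger change SD (2.65–5.42 against 2.64–5.17) and a reported IPSS improvement smaller by the 0.1–1.8 points of bias removed. With correlated errors part of the bias stays, about 0.5–0.9 of 1.8 points in the worst setting at correlations of 0.3–0.5.

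3. Add that a man without the separate form is analysed with his qualifying form, flagged in the report, and left out in a sensitivity analysis. Each such man puts back an expected 1.78/10 = 0.18 points in the mean of 10 in the worst setting, and less elsewhere.

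### Adverse events are a primary outcome, but the plan lists no general adverse-event item, contact schedule or severity scale, so the safety count is at risk of under-ascertainment

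*Combined protocol and SAP*

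**What the plan says.** The list of primary outcomes opens with "Primary outcome measures at baseline, 2 months, 4 months, 6 months and 24 months", and its fifth item is "Number and severity of adverse events". Safety therefore has the same rank and timing as the four questionnaire outcomes.

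Under Data Collection, "Patients will complete the follow-up surveys at home and mail, fax, or scan and e-mail them in". The content of those forms is given next: "They will fill up survey forms related to their SHIM, IPSS with QOL, and BPH Impact Index". No adverse-event form or question is named.

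Under Monitoring and reporting of Adverse Events, the investigator "will monitor all adverse events". Further on, "The principal investigator and his staff will be in regular communication with patients", and "patients will be instructed to self report adverse events". The Risk / Safety Information section adds that the investigator will manage complications and bring in other specialties where needed.

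The available text does not state how often patients are contacted, what they are asked, what period they are asked to recall, or how severity is graded. The Statistical Analysis section covers survey results only and gives no summary for adverse events.

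**The concern.** Four primary outcomes have a named instrument and a fixed schedule. The fifth has a schedule but no named way of asking and no grading scale. Benefit is prompted in a standard way four times after ablation. General harm depends on what a man at home decides to report and on contact whose content is left open.

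A man may think an event normal after a procedure, have it treated elsewhere, or forget it. Each such loss lowers the safety count, and none raises it. With 10 men and no comparator in which events would be missed equally, one or two lost events could change how the published safety result reads. The Intended Use of Data section foresees publication in a journal and on ClinicalTrials.gov.

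The missing severity scale is a related but separate gap. It does not lower the count; it means that the severity half of the outcome cannot be reproduced by a second grader.

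**Working it through.** The documents give no event rate, capture rate or adverse-event analysis, so there is no stated figure to reproduce. The check has three parts.

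**1. Primary outcomes side by side**

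| Primary outcome | Instrument named | Planned analysis |
|---|---|---|
| 1. IPSS | yes | repeated-measures ANOVA and pairwise p-values |
| 2. IPSS quality-of-life question | yes | same |
| 3. BPH Impact Index | yes | same |
| 4. SHIM | yes | same |
| 5. Adverse events, number and severity | no form, no question set, no scale | none stated |

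IPSS and SHIM would show worse urinary or erectile function. No rule turns a worse score into an adverse event or a severity grade. Neither is a general harms form: events from the transrectal route, the sedation or the gadolinium contrast have no item that asks for them.

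**2. Timing**

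The first post-baseline form is due at month 2, so nothing is scheduled in the weeks just after ablation. Between the last two forms there are 24 − 6 = 18 months. In both windows collection rests wholly on self-report, monitoring and contact whose timing is not stated.

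**3. What incomplete capture would do (illustration, assumed inputs)**

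From the protocol: n = 10 men, one arm. Assumed, with no source in the documents: the true risk *p* that a man has a given event, and the probability *s* that such an event reaches the study record by any route. Men are treated as independent.

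- Expected number of men recorded = 10 × *p* × *s*
- P(none recorded) = (1 − *p* × *s*)^10

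| *p* | *s* | Expected men recorded | P(none recorded) |
|---|---|---|---|
| 30% | 100% | 3.0 | 0.70^10 = 2.8% |
| 30% | 75% | 2.25 | 0.775^10 = 7.8% |
| 30% | 50% | 1.5 | 0.85^10 = 19.7% |
| 20% | 100% | 2.0 | 0.80^10 = 10.7% |
| 20% | 75% | 1.5 | 0.85^10 = 19.7% |
| 20% | 50% | 1.0 | 0.90^10 = 34.9% |

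The same effect can be read from the interval. If no man of 10 has a recorded event, the exact one-sided 95% upper bound on the *recorded* risk is 1 − 0.05^(1/10) = 25.9%. The recorded risk is *p* × *s*, so the bound on the true risk is 25.9% / *s*:

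- *s* = 100%: 25.9%
- *s* = 75%: 0.2589 / 0.75 = 34.5%
- *s* = 50%: 0.2589 / 0.50 = 51.8%

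The direction follows from the definition, since *s* cannot exceed 1. The value of *s* does not follow from anything in the documents.

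**The case against.** A reader might infer that adverse events are collected only by unprompted self-report, that harm is never asked about, and that the safety count is therefore biased downward. The documents do not support this.

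- Self-report is one route among several. The same sentence promises contact by the investigator and staff, the paragraph promises monitoring, and complications managed by the investigator will reach him. The text does not say that reporting is unprompted. These routes are unspecified, not absent.
- SHIM and IPSS ask in a standard way about two domains where harm is plausible here.
- Nothing shows that events would be missed at any particular rate. The capture values are assumed, and no decision in the plan hangs on recording zero events, so the table illustrates the mechanism without measuring an effect on a planned conclusion.
- The protocol refers to procedure and sedation consent forms that describe the risks. Those pages are not in the public text and may tell men what to report.
- Grading by the treating investigator is not in itself an error in a 10-man, single-center study.

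All of this stands, and it limits the claim. It does not remove the gap. A route with no stated schedule or questions cannot be repeated or audited, an event treated elsewhere need not reach the investigator, and questionnaire scores do not become adverse events under any stated rule. Instructions in a consent form would improve self-report but would not amount to scheduled, standard questioning.

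**Conclusion.** The concern holds in a limited form. A primary outcome lacks a specified method of elicitation, a severity scale and an analysis. The count is at risk of under-ascertainment, and any loss makes the procedure look safer. That the count *is* biased is not shown.

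The size cannot be derived from the documents. Under assumed true risks of 20% to 30%, a fall in capture from 100% to 50% halves the expected count. It raises the chance of recording none in 10 men from 10.7% to 34.9% (20% risk) or from 2.8% to 19.7% (30% risk). These figures rest on assumed risk and capture, and on independence between men.

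The sponsor should make the change. It is a cheap improvement to how a primary outcome is measured; the outcome is already collected in some manner, so the point is not fatal to the study.

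**What to change.** - Add a one-page fixed adverse-event checklist to the packet already returned at 2, 4, 6 and 24 months. Use yes/no and date items drawn from the risks in the study's own consent forms, plus any unplanned doctor, emergency or hospital visit since the last form.
- Have the same page completed at baseline, so that pre-existing complaints can be told apart from new events.
- State how often the planned staff contact takes place and ask the same questions then, in particular before month 2 and between months 6 and 24. This limits reliance on long recall.
- Grade every event on one named published severity scale, fixed before the first ablation.
- State whether a worse SHIM or IPSS score counts as an adverse event.
- Add an analysis: the number of men with at least one event out of 10, overall and by severity, with an exact interval. For 0 of 10, the two-sided 95% upper limit is 1 − 0.025^(1/10) = 30.8%.
- Keep self-report as an additional source.

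The cost is a protocol amendment, one page in an existing mailing and some staff time in contacts already planned, with no extra visit. The downside is that prompted questions will record more minor events, so the safety figure will look less favourable. By how much cannot be said from the documents.
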